## 1.0 Objectives

### 1.1 Study Objectives

Describe the purpose, specific aims or objectives. State the hypotheses to be tested.

In this study, we propose a prospective trial to determine if contrast enhanced ultrasound (CEUS) is non-inferior to CT or MRI in patients with hepatocellular carcinoma (HCC) following transcatheter arterial chemoembolization (TACE) treatments, in a U.S. population, using Lumason contrast agent. This would be the largest trial to date examining this patient population in the U.S.

The primary objective of our study is to estimate the sensitivity and specificity of the CEUS (Research Timepoint 1) and evaluate for non-inferiority between CEUS and the clinical gold standard of CT/MRI using the Liver Reporting & Data System (LIRAD). We will be assessing the presence of treated or residual tumor, new sites of disease, and portal vein thrombus. Patient factors, such as BMI, underlying liver disease type, alpha fetoprotein level, and size of liver will be recorded. If findings of metastatic disease external to the liver are identified on CT or MRI and not seen on CEUS, they will be recorded.

CEUS, like regular ultrasound, only images specific organs and cannot identify necessarily metastatic disease, as ultrasound cannot image bones and lungs for this purpose.

The second objective of the project will compare the CEUS with a second, standard of care, follow-up CT or MRI (performed 2-4 months later [Research Timepoint 2]). CT can have false negatives due to ethiodol obscuring subtle, early disease and it is possible that CEUS could identify residual disease earlier compared to the gold standards, but would be characterized as a false positive if compared only to the initial imaging (Timepoint 1). This follow-up will evaluate for false positives or negatives on any of the modalities.

The third objective of the project will evaluate patient subjective data in regards to imaging modality preference and possible effects on compliance. The survey will be administered at the conclusion of Timepoint 1 and will include questions about anxiety, comfort, compliance, and modality preference, graded on a Likert scale.

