### 1.2 Primary Study Endpoints

State the primary endpoints to be measured in the study.

Clinical trials typically have a primary objective or endpoint. Additional objectives and endpoints are secondary. The endpoints (or outcomes), determined for each study subject, are the quantitative measurements required by the objectives. Measuring the selected endpoints is the goal of a trial (examples: response rate and survival).

- Non-inferiority between CEUS and the patient's routine CT/MRI, which occurs 2-4 months after TACE treatment (Research timepoint 1). Additionally endpoints that will be measured include treated, residual, or new tumor present on the follow-up.
- The second routine follow-up of CT/MRI (timepoint 2) will be compared to exclude false positives/negatives in the first follow-up imaging (timepoint 1), which occurs approximately 2-months after the first imaging visit.
- Patient subjective data – through the use of a patient survey, given after the first follow-up (Research timepoint 1), where patient had CEUS and CT/MRI (2-4 months after TACE treatment).

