### 2.2 Previous Data

Describe any relevant preliminary data.

In unpublished work (CATS IRB STUDY00014728) presented at the 2019 Society of Radiologists in Ultrasound annual national meeting, our group presented on our experience in imaging liver patients with CEUS (19). At the time of presentation, 62 patients had been imaged, with 16% yielding a positive finding. Our group correctly diagnosed all lesions – all malignant lesions and vascular thrombi had confirmation via gold standard imaging of CT or MRI, or on explanation; benign lesions were confirmed by stability on follow-up imaging. Our study also evaluated patient factors that resulted in limited visualization with CEUS, which included severe steatosis and/or increased abdominal adiposity. In addition, at our institution, we have utilized CEUS in several patients post-TACE, which were subsequently shown to correctly diagnosis residual tumor by follow-up MRI and/or TACE (unpublished). If one were able to accurately and reliably use CEUS to determine residual tumor after TACE, this would decrease the need for CT scans (which have the risk of radiation and contrast-enhanced nephropathy) and MRI scans (which are very expensive and are difficult to perform in patients with claustrophobia).

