### 3.1 Inclusion Criteria

Create a numbered list of the inclusion criteria that define who will be included in your final study sample (e.g., age, gender, condition, etc.)

1. Adult ( $\geq 18$  years of age) patients with diagnosed HCC, who are treated with their first round of TACE.
2. Sex: male or female
3. BMI  $\leq 40$

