## 7.2 Study Procedures

Provide a step by step description of all research procedures being conducted (broken down by visit, if applicable) including such information as below (where and when applicable); describe the following:

- HOW: (e.g., data collection via interviews, focus groups, forms such as surveys and questionnaires, medical/school records, audio/video/digital recordings, photographs, EKG procedures, MRI, mobile devices such as electronic tablets/cell phones, observations, collection of specimens, experimental drug/device testing, manipulation of behavior/use of deception, computer games, etc.)
- WHERE: (e.g., classrooms, labs, internet/online, places of business, medical settings, public spaces, etc.)

Subject demographics, disease state, and tumor characteristics, CT/MRI and CEUS results will be recorded and entered in REDCAP and Oncore.

### 7.2.1 Timepoint 0

Provide a description of what procedures will be performed on visit 1 or day 1 or pre-test in order of how these will be done. If your study only involves one session or visit, use this section only and indicate 7.2.2 as not applicable.

Our proposed study population includes subjects with diagnosed HCC, who are treated with TACE. Patients will be identified and enrolled at the time of initial TACE.

### 7.2.2 Timepoint 1

Provide a description of what procedures will be performed on visit 2 or day 2 or post-test in order of how these will be done. If your study involves more than two sessions or visits replicate this section for each additional session or visit (e.g., 7.2.3, 7.2.4, etc.).

Following initial TACE, patients will receive a CT or MRI, as routinely ordered in the post-TACE setting, to assess for residual or new HCC. The timing of this follow-up occurrence will be followed as routinely ordered by the patients' providers and not be decided upon or affected by involvement in the trial. At this same imaging follow-up visit, patients will also receive a one-time additional contrast-enhanced ultrasound (CEUS). This visit will be performed at either the main hospital or our East Campus, depending on availability and patient needs. MRI, CT, and CEUS will be completed at the same location (i.e., both CT/MRI & CEUS will be completed at either the main hospital or East campus), allowing patient convenience and privacy to simply move between rooms for both exams.

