### 8.3 Statistical methods

Describe the statistical methods (or non-statistical methods of analysis) that will be employed.

Patient demographics and major clinical information described above will be summarized using descriptive statistics. The main outcome variables in primary objective are the incidence of residual tumor and new tumor, which are both binary. The rate of residual/new tumors using CEUS and CT/MRI will be compared using McNemar's test, which is suitable for comparing paired binary variables. The point estimate and 95% confidence interval (CI) of the incidence rate for CEUS and CT/MRI will be reported separately. Due to the limited sample size of this pilot study, the non-inferiority between CEUS vs CT/MRI will be evaluated just by comparing the CIs of the incidence rate for each method, not by a formal statistical non-inferiority test which requires a much larger sample size. A few additional subgroup analyses will be performed to see if the incidence rate varies by stratification (such as BMI group, liver disease type). Due to the exploratory nature of this study no multiple regression models will be used, and no adjustment of the alpha rate will be made due to multiple testing. Treating the CT/MRI as the clinical gold standard, the sensitivity and specificity of CEUS will be estimated with their 95% CIs. The data from secondary objective will be analyzed similarly as those for the primary objective. For tertiary objective, the subjective ratings from patients between the CT/MRI and ultrasound will be compared using nonparametric Wilcoxon Signed-rank tests. The ratings may be further correlated with some of the baseline demographic and clinical factors using nonparametric Kruskal-Wallis tests. All analyses will be performed using statistical software SAS version 9.4 or higher (SAS Institute, Cary, NC, USA). All tests are two-sided and the significance level to be used is 0.05.

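### On its natural reading, Section 8.3 scores Timepoint 1 CEUS against a CT/MRI taken about 2-4 months later by a same-visit method, so tumour arising in between counts as a CEUS false negative

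*Combined protocol and SAP*

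**What the plan says.** Section 1.1 states: "The second objective of the project will compare the CEUS with a second, standard of care, follow-up CT or MRI", placing that scan 2-4 months later. The reason given is that ethiodol can hide early disease on CT, so a true CEUS finding might look like a false positive against the Timepoint 1 scan alone. It adds: "This follow-up will evaluate for false positives or negatives on any of the modalities". Section 1.2 likewise uses the later scan to rule out Timepoint 1 errors. Section 7.2.3 leaves its timing to the treating physicians.

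For the primary objective, Section 8.3 names residual tumour and new tumour as binary outcomes. It compares the CEUS and CT/MRI rates by McNemar's test, gives a confidence interval for each rate, and then says: "Treating the CT/MRI as the clinical gold standard, the sensitivity and specificity of CEUS will be estimated with their 95% CIs". For the second objective it says only: "The data from secondary objective will be analyzed similarly as those for the primary objective".

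Section 7.2.2 places the primary CEUS and CT/MRI at the same imaging visit.

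**The concern.** A method built for two scans at one visit can treat every disagreement as test error. With months between scans, disagreement also arises because the disease has changed. Section 8.3 carries the first method over to the second setting and adds nothing on a lesion first seen at Timepoint 2, on treatment between the scans, or on matching lesions across time. Sections 1.1 to 1.3, 3.3 and 7.1 to 7.3 do not fill the gap.

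Timepoint 2 is the only check the documents provide on a Timepoint 1 reference that Section 1.1 says can be falsely negative on CT. If that check mixes test error with disease course, the second objective is not answered. Section 8.2 intends the pilot data for a formal power calculation and a larger grant submission, so a distorted accuracy figure could be carried forward.

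**Working it through.** **Which objective the instruction covers.** Section 1.3 lists patient and tumour predictors as secondary endpoints. But 8.3 gives the patient ratings to the tertiary objective, and these are the third objective in 1.1. Its secondary objective is therefore most naturally the second in 1.1: Timepoint 1 CEUS against Timepoint 2 CT/MRI.

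**Inputs.** The documents give N = 34 (8.1, 8.2) and no rates of residual, new or cleared tumour. Every count below is assumed. CEUS is taken as perfect at Timepoint 1 and the Timepoint 2 scan as error-free, so the true error is zero.

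**Interval tumour.** Take a pooled residual/new outcome with 14 positive and 20 negative patients (14 + 20 = 34). If k negatives develop tumour before Timepoint 2, apparent sensitivity = 14/(14 + k):

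- k = 2: 14/16 = 88%
- k = 4: 14/18 = 78%
- k = 6: 14/20 = 70%

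As proportions, with prevalence p and new tumour in a fraction q of negatives, apparent sensitivity = p/[p + (1 − p)q]. For p = 0.4 and q = 0.2 this is 0.4/0.52 = 77%. Over p = 0.3 to 0.5 and q = 0.1 to 0.2 it runs from 0.3/0.44 = 68% to 0.5/0.55 = 91%.

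A perfect Timepoint 1 CT/MRI would also score 14/18 for k = 4, so the difference between tests would be zero. Because 8.3 scores CEUS alone, that cannot be seen.

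**Pooling matters.** Section 8.3 can be read as keeping residual and new tumour separate. New tumour elsewhere in the liver would then leave residual-tumour sensitivity unchanged, and only regrowth at the treated site would lower it. The new-tumour outcome would carry the whole effect.

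**Cleared tumour (conditional).** If k tumours that CEUS correctly found were treated and cleared, apparent specificity = 20/(20 + k): for k = 4, 20/24 = 83%.

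**McNemar's test.** With b discordant pairs all in one direction, the exact two-sided p is 2 × 0.5^b: 0.125 for 4 v 0 and 0.031 for 6 v 0. For 4 new and 4 cleared (4 v 4), p = 1.0. The test can show a difference or none, with no test error in any of these cases.

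**Why not just exclude treated patients.** Assume both tests are truly 90% sensitive and specific, prevalence 50%, independent errors, and half of CT/MRI-positive patients treated. As fractions of all patients:

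- Untreated tumours: 0.225 CT/MRI-positive + 0.05 CT/MRI-negative = 0.275.
- After exclusion, CT/MRI sensitivity = 0.225/0.275 = 82%, and CEUS = 0.2475/0.275 = 90%. Two equal tests differ by 8.2 points.
- Counting all the treated (0.205 CEUS-positive + 0.045 CEUS-negative = 0.25) as tumour instead: CEUS (0.2475 + 0.205)/0.525 = 86.2%, CT/MRI (0.225 + 0.25)/0.525 = 90.5%, a difference of −4.3 points.

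**Interval wording.** Section 1.1 puts Timepoint 2 2-4 months later. Section 1.2 says about 2 months after the first imaging visit, and 7.2.3 says typically 2-4 months after it. Section 1.2 puts Timepoint 1 at 2-4 months after TACE. TACE to Timepoint 2 would then be 2 + 2 = 4 to 4 + 4 = 8 months, while 7.3 gives total participation of about 4 months.

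**The case against.** The delayed check is deliberate: Section 1.1 gives a sound reason why a later scan may vindicate an early CEUS positive. That stands, but it does not say how to tell missed tumour from tumour that arose afterwards.

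The criticised analysis is partly inferred, since 8.3 says similarly, not identically, and does not spell out McNemar's test for Timepoint 2. That is why the point is put as the natural reading. No other method is offered.

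A reader might infer that patients are treated between the scans and that the study fails to record it. The documents do not support that. Eligibility concerns patients "who are treated with their first round of TACE", and Section 2.2 describes earlier CEUS cases "subsequently shown to correctly diagnosis residual tumor by follow-up MRI and/or TACE". Together with Timepoint 1 CT/MRI results reaching the medical record (Section 12.0), these make interim treatment plausible; they do not establish it or its frequency. On recording, Section 7.2 says: "Subject demographics, disease state, and tumor characteristics, CT/MRI and CEUS results will be recorded and entered in REDCAP and Oncore". Interim treatment is not named, but disease state is, and the case report form mentioned in Section 9.3 is not among the documents.

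Precision is also poor at this size: the exact 95% interval is 77-100% for 14/14 and 52-94% for 14/18. Modest bias would be hard to tell from chance. This limits what the pilot can show, but it does not justify scoring real change as error. A full analysis over every possible status of treated patients would be out of proportion here, as would site-level scoring, which leaves clustering and the negative denominator for new tumour undefined.

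**Conclusion.** The concern holds for the second objective. Followed as written, on the natural reading, tumour arising after a correct negative CEUS is scored as a false negative; this needs no assumption about treatment. Misscoring of cleared tumour is a weaker, conditional concern. The restriction of accuracy to CEUS falls short of what Section 1.1 promises.

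The size is unknown. The 78% figure (70-88% for two to six interval tumours) rests on assumed counts, a perfect CEUS, an error-free later scan and a pooled outcome or regrowth at the treated site.

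A reader might go further and conclude that the primary result is compromised, or that the bias favours one modality. Neither follows: the primary comparison is same-visit, and the documents give no basis for a direction between CEUS and CT/MRI. This is a secondary analysis in an exploratory pilot and should be corrected before Timepoint 2 data are analysed.

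**What to change.** In Section 8.3, replace the single sentence on the second objective with a per-patient plan:

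1. Do not use McNemar's test, or the rate comparison, of Timepoint 1 CEUS with Timepoint 2 CT/MRI as evidence of a difference between tests.
2. Score Timepoint 1 CEUS and Timepoint 1 CT/MRI against the same Timepoint 2 reference. State that CT errors shared across timepoints, such as those from ethiodol, may favour CT/MRI.
3. Report residual tumour at the treated site separately from new-site tumour. Report tumour first seen at Timepoint 2 and negative on both Timepoint 1 tests as interval disease, with a sensitivity analysis counting it as missed by both.
4. Abstract from the chart any liver-directed treatment between the timepoints and tabulate results by it. Do not simply exclude treated patients. A simple sensitivity analysis is enough, for example counting them all as tumour and then all as no tumour, with a note that these two results are not strict limits on the difference between tests.

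Reconcile the interval wording in Sections 1.1, 1.2, 7.2.3 and 7.3.

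The cost is one extra chart item, some matching of Timepoint 2 findings to the treated site, and a little more analysis. No study procedure is added. The secondary estimates will be wider or more qualified.

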### 1.3 Secondary Study Endpoints

State the secondary endpoints to be measured in the study.

To determine if patient or tumor characteristics (BMI, pre-treatment alpha feta protein levels, size of tumor treated) are predictive of whether CEUS is non-inferior to CT/MRI or in which cases it may not be, due to the limitations of ultrasound as a modality.

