### 8.0 Subject Numbers and Statistical Plan

#### 8.1 Number of Subjects

Indicate the maximum number of subjects to be accrued/enrolled. Distinguish between the number of subjects who are expected to be enrolled and screened, and the number of subjects needed to complete the research procedures if applicable (i.e., numbers of subjects excluding screen failures.)

We plan to enroll 34 subjects.

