#### 8.2 Sample size determination

If applicable, provide a justification of the sample size outlined in section 8.1 to include reflections on, or calculations of, the power of the study.

Planned sample size = 34

Presently there is no data available to suggest how large an effect size may exert on the primary outcome measures. Accordingly, a formal sample size calculation was not done as the goal of this pilot study is to: 1) assess the feasibility of the study design, 2) generate data needed for a formal power calculation, and 3) generate pilot data for larger-scale grant submission. Based on the availability of patients, feasibility of our operations, we plan to recruit 34 patients. We believe this sample will serve our purpose well as a pilot study with plans to include further patients as funding allows.

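### If continuous baseline factors are related to the survey ratings, Kruskal-Wallis ignores order, gives no correlation estimate and has less power than a rank correlation for a monotone relation

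*Combined protocol and SAP*

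**What the plan says.** The third objective (section 1.1) is a patient survey at the end of Timepoint 1, which "will include questions about anxiety, comfort, compliance, and modality preference, graded on a Likert scale". The number of rating levels is not given. Section 8.3 compares the ratings between CT/MRI and ultrasound by the Wilcoxon signed-rank test and then adds: "The ratings may be further correlated with some of the baseline demographic and clinical factors using nonparametric Kruskal-Wallis tests".

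That sentence names no factor and no grouping. The nearest list is in section 1.1, in the paragraph on the primary objective: "Patient factors, such as BMI, underlying liver disease type, alpha fetoprotein level, and size of liver will be recorded". Three of those four are continuous, and liver disease type is categorical. Section 1.3 refers to "patient or tumor characteristics (BMI, pre-treatment alpha feta protein levels, size of tumor treated", but for the comparison of CEUS with CT/MRI and not for the survey. Grouping appears elsewhere in 8.3, for tumor incidence: "A few additional subgroup analyses will be performed to see if the incidence rate varies by stratification (such as BMI group, liver disease type". No BMI cut-points are given there.

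On size and level: "We plan to enroll 34 subjects" (section 8.1) and "All tests are two-sided and the significance level to be used is 0.05" (section 8.3). There is no power target, because "a formal sample size calculation was not done as the goal of this pilot study is to" assess feasibility and produce pilot data (section 8.2).

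**The concern.** The stated aim is to correlate, but the stated tool compares groups. Kruskal-Wallis asks whether the distribution of one variable differs across unordered groups. It gives no coefficient, direction or confidence interval, and it makes no use of any order among the groups.

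That suits liver disease type. For a continuous factor there are two ways to apply it:

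- Cut the factor into groups and compare ratings across them. The plan gives no cut-points, so the result would depend on a choice that could be made after the data are seen.
- Use the rating levels as groups and compare the uncut factor across them. No cut-points are needed, but the order of the Likert levels is discarded.

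With 34 patients at most, the question is how much information each route loses compared with a rank correlation, which uses the order of both variables.

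**Working it through.** The documents give no power, effect size or derived sample size for this analysis, so there is no figure to reproduce. The check compares the power of the candidate tests.

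**Inputs from the documents:** n = 34 (8.1); two-sided 0.05 (8.3); ordinal Likert outcome (1.1).

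**Assumed inputs, not in the documents:** a 5-level rating; a standard normal factor x; latent correlation ρ from 0.3 to 0.6; analysed numbers of 29 and 24 as well as 34. Section 3.3.1 allows removal but gives no rate. The normality of x matters little for a skewed factor such as alpha fetoprotein, because ranks and quantile groups do not change under a monotone transformation of the factor.

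**Model.** Latent score s = ρx + √(1 − ρ²)·e, with e standard normal. The rating is s cut at −1.28, −0.52, 0.25 and 0.92. There were 6,000 replicates per setting, so the Monte Carlo standard error is at most √(0.25/6000) = 0.0065, or about 0.6 points.

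**Tests.** Spearman; Kruskal-Wallis (KW) with x cut into 2, 3 or 4 equal groups; KW of the uncut x across rating levels.

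Rejection rate (%), monotone relation:

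| n | ρ | Spearman | KW, 2 groups | KW, 3 groups | KW, 4 groups | KW by rating level |
|---|---|---|---|---|---|---|
| 34 | 0 | 5.4 | 5.3 | 4.8 | 4.2 | 3.8 |
| 34 | 0.3 | 35.8 | 24.6 | 22.2 | 18.7 | 16.3 |
| 34 | 0.4 | 59.2 | 41.5 | 38.4 | 34.5 | 31.2 |
| 34 | 0.5 | 81.0 | 62.4 | 60.3 | 54.8 | 53.1 |
| 34 | 0.6 | 93.9 | 80.9 | 80.5 | 76.9 | 77.0 |
| 29 | 0.5 | 74.2 | 54.8 | 53.2 | 47.5 | 43.1 |
| 24 | 0.5 | 63.4 | 45.4 | 41.4 | 36.7 | 31.6 |

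The ρ = 0 row shows that Spearman's advantage is not bought with an inflated type I error. At n = 34 the loss from cutting the factor runs from 35.8 − 24.6 = 11.2 points (ρ = 0.3, median split) to 81.0 − 54.8 = 26.2 points (ρ = 0.5, quartiles). Repeat simulations at n = 34 and ρ = 0.5 gave 81% for Spearman, 61-64% for KW on a median split and 60-61% on tertiles.

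**Analytic check on Spearman.** Power ≈ Φ(atanh(ρ)·√((n − 3)/1.06) − 1.96). For ρ = 0.5 and n = 34: 0.5493 × √(31/1.06) = 0.5493 × 5.408 = 2.971; 2.971 − 1.96 = 1.011; Φ(1.011) = 0.844. That is before the score is coarsened to five levels, and it is consistent with the simulated 81.0%.

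**Non-monotone case.** With s driven by (x² − 1)/√2 at strength 0.5 and n = 34, Spearman rejects in 7.1%. KW rejects in 6.2% (2 groups), 17.6% (3), 21.2% (4) and 5.1% (by rating level). Here the ranking reverses, but only when the factor is cut into three or four groups.

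**The case against.** The strongest reply is that the sentence promises very little. It says the ratings may be correlated with some factors. If the factors chosen are liver disease type or sex, Kruskal-Wallis is a proper test and there is nothing to correct. Grouping is also the plan's own habit, as with the BMI groups for tumor incidence, so analysing ratings by the same strata would be coherent even if less efficient. All of this stands, and it makes the point conditional on continuous or ordinal factors being used.

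A reader might infer that the plan commits to cutting BMI, alpha fetoprotein and size into groups. The documents do not say so. The sentence names no factor, the analysis is optional, and the rating levels could serve as the groups with the factor uncut. That last route avoids cut-points but not the loss of power (53.1% at ρ = 0.5).

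It is also fair to say that the power figures rest on assumed inputs, that the advantage disappears for a U-shaped relation, and that at ρ = 0.3 Spearman itself reaches only about 36%. The change improves the analysis without making it well powered.

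Finally, a reader might infer that the later trial would be left without a needed effect size. Section 8.2 links the missing effect size to the primary outcome measures, and nothing says that associations between survey ratings and baseline factors will size a later study.

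**Conclusion.** The point holds in conditional form. If continuous or ordinal factors are related to the ratings, the only named test ignores order, yields no correlation estimate, and for a monotone relation loses roughly 11 to 26 points of power at n = 34 when the factor is cut into two to four groups. This rests on a 5-level rating, a latent correlation of 0.3 to 0.6 and a monotone relation, none of which the documents supply. The word correlated makes a monotone question the natural reading, but it does not guarantee one.

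The consequence is small. Section 1.2 lists the survey under its primary endpoints heading, so a reader might take this as touching the primary analysis. It does not: 8.3 handles the ratings under the tertiary objective, and relating them to baseline factors is an optional further step. The McNemar comparison, the sensitivity and specificity estimates and the paired Wilcoxon test are all unaffected.

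**What to change.** Replace the sentence in 8.3 with wording such as: *Associations between survey ratings and continuous or ordinal baseline factors will be described by Spearman's rank correlation with a 95% confidence interval, with a scatterplot to look for non-monotone patterns. Kruskal-Wallis tests will be used for unordered categorical factors such as liver disease type.*

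It would help to name the factors in the same place and, if any grouping of a continuous factor is kept, to fix its cut-points before the data are seen.

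The cost is a few lines of text. The data are already to be collected, and the SAS software named in 8.3 covers the analysis. No extra patients or procedures are needed.
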